In principle, a patient needs to be on study for at least 28 days to be evaluable for DLT observation, and may be replaced if they terminate study participation earlier than 28 days without experiencing a DLT. Patients who are not able to receive at least 80% of the planned dose of the PF-06747143 and backbone chemotherapy (in Part 2 combination study) in the DLT assessment period are considered not evaluable for DLT and will be replaced. However, in some circumstances of a clear drug unrelated event (eg, traffic accident, clear disease progression, or withdrawal of consent) that leads to study termination close to or before 28 days, the patient might be deemed evaluable if the Investigators and Sponsor agree.

In addition, patients not evaluable for assessment of DLT, as described in Section 7.2.1, may be replaced.

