#### **Treatment Administration/Compliance**

Listings and tables by dose level will be provided. Cycle length is 21 days. Day 1 of a cycle is the first date of dose within that cycle. The safety analysis set will be used.

Dose modifications may occur in the following ways:

- Cycle delay—Day 1 of current cycle starts later than 21 days from Day 1 of the previous cycle (only applies to cycle 2 and above);
- Dose reduction—A decrease in the administered total daily dose (non-zero) compared to the planned total daily dose upon enrollment. If in the CRF the prescribed dose unit is mg/kg, but the actual dose is in mg the actual dose mg/kg should be calculated considering the body weight of the patient at that visit.

Intra-patient dose escalation is not allowed in this study. The following will be summarized by subject for each dose level:

- Number of subjects per dose level;
- Median and range of number of cycles started per subject;
- Number (%) of subjects starting a cycle (1, 2, 3...);
- Number (%) of subjects with cycle delays;
- Number (%) of dose interruptions (include both known and unknown dates);
- Number (%) of subjects with dose reductions:
- Number (%) of each reason (AE vs. Other) for cycle delays, dose interruptions and dose reductions;

• Time on treatment (median, range).

The following will be summarized by cycle received for each dose level:

- Total number of cycles started;
- Number of cycles started per subject (median, range);
- Number of cycles before 1st delay (median, range);
- Number of cycles before 1st reduction (median, range);
- Number of cycles before 1st interruption (median, range).

The following will be summarized for cumulative dose by dose level and cycle:

• Summary statistics (mean, median, standard deviation and range) of cumulative dose and percent of starting dose (compared to Day 1 dose of each cycle)

Listings by subject (ordered by dose level): start date and stop date of each dosing period within each cycle (including records with 0mg), administered total daily dose for each period, any missed doses with unknown dates (Y/N), number of missed doses with unknown dates, reason for any dosing changes.

Listings by subject and each cycle (ordered by dose level): cycle length, total planned dose, administered total dose, percentage of planned dose, dose delay (yes/no), dose reduction (yes/no), and dose interruption (yes/no).

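### The only summarised relative-dose percentage is re-based to each cycle's own Day 1 dose, so a reduction already in force on Day 1 does not show in it

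*SAP*

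**What the plan says.** The text is in SAP 9.2.4, Treatment Administration/Compliance. Under the lead-in "The following will be summarized for cumulative dose by dose level and cycle" it asks for two things: "Summary statistics (mean, median, standard deviation and range) of cumulative dose", and "percent of starting dose (compared to Day 1 dose of each cycle"). The start of a cycle is fixed by "Day 1 of a cycle is the first date of dose within that cycle".

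The same section uses a different reference when it defines a dose reduction: a lower non-zero dose "compared to the planned total daily dose upon enrollment". It also plans several other displays that bear on reductions:

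- "Number (%) of subjects with dose reductions", with the reason (adverse event or other);
- "Number of cycles before 1st reduction (median, range");
- a listing by subject and cycle with the planned and administered totals, the percentage of planned dose, and yes/no flags for delay, reduction and interruption.

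Elsewhere, 2.1.1.2 allows a patient with a DLT to be managed by dose modification after an interruption, so reduced dosing in later cycles is foreseen. Section 7.2.4 links the RP2D to whether the MTD is feasible over long-term administration.

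**The concern.** A relative-dose statistic should tell the reader how much of the intended dose was delivered. That requires a reference that does not move when the dose is modified. Here the reference is the first dose of the same cycle. Once a patient starts a cycle at a reduced level, the reduced level becomes the new 100%.

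This gives two references within one section. A patient can be counted as dose-reduced in one table, against the enrollment dose, and show 100% for the same cycle in the next. The label adds to the difficulty, because most readers would take starting dose to mean the dose at study start.

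At stake is the description of tolerability in later cycles. Treatment may run to about 12 cycles in Cohort 2 (2.2.2.2), and through induction, consolidation and up to 6 maintenance cycles in Cohort 1 (2.2.2.1). Sustained delivery of the intended dose is the question that 7.2.4 raises, and this percentage does not address it for patients whose dose was lowered.

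**Working it through.** The SAP states no figure that could be reproduced, so the check compares the two references on constructed dosing histories.

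**Inputs**
- Planned weekly dose: 1 unit (scale only).
- Doses per cycle: 4, from weekly dosing in 28-day cycles (SAP 2.1.1).
- Follow-up: 4 cycles (assumed).
- Reduced dose f: 90%, 75% or 50% of planned. The SAP gives no reduction size, so these values are assumptions that show the range.

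**Formulas**
- A, the plan's percentage as naturally read: dose given in the cycle ÷ (4 × that cycle's Day 1 dose).
- B, fixed reference: dose given in the cycle ÷ (4 × dose planned at enrollment).

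**Case 1: reduction from Cycle 2 Day 1, all doses given.** In Cycles 2 to 4 the dose given is 4f.
- A = 4f ÷ 4f = 100%, whatever the value of f.
- B = 4f ÷ 4 = f.

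| f | A, Cycles 1–4 | B, Cycles 1–4 | B over 4 cycles |
|---|---|---|---|
| 90% | 100/100/100/100 | 100/90/90/90 | 14.8/16 = 92.5% |
| 75% | 100/100/100/100 | 100/75/75/75 | 13/16 = 81.2% |
| 50% | 100/100/100/100 | 100/50/50/50 | 10/16 = 62.5% |

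Over 6 cycles with f = 75%, B overall is (1.00 + 5 × 0.75) ÷ 6 = 4.75 ÷ 6 = 79.2%, against 100% in every cycle under A. The absolute cumulative dose does fall, to 4, 3, 3 and 3 units over four cycles at f = 75%.

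**Case 2: reduction to 75% at the third dose of Cycle 2, then held.**
- Cycle 2 dose given: 1 + 1 + 0.75 + 0.75 = 3.5, so A = 3.5/4 = 87.5%.
- A by cycle: 100/87.5/100/100. The reduction shows once and then drops out.
- B by cycle: 100/87.5/75/75, overall 13.5/16 = 84.4%.

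**Case 3: reduction to 75% from Cycle 2 Day 1, with one dose omitted in Cycle 3.**
- Cycle 3 dose given: 3 × 0.75 = 2.25. A = 2.25 ÷ 3 = 75%; B = 2.25 ÷ 4 = 56.2%.
- A by cycle: 100/100/75/100. The omission shows and the reduction does not.
- B by cycle: 100/75/56.2/75, overall 12.25/16 = 76.6%.

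**Cycle length.** Section 9.2.4 states a 21-day cycle; 2.1.1, 2.1.1.1 and the Part 2 description state 28 days. With weekly dosing these imply 21/7 = 3 and 28/7 = 4 planned doses per cycle. One omitted dose would then read 2/3 = 66.7% or 3/4 = 75% of plan. Any percentage of planned dose depends on which length applies.

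**The case against.** The strongest reply is that 9.2.4 does report reductions. It counts patients with reductions, gives reasons, summarises the cycles before the first one, summarises absolute cumulative dose by dose level and cycle in the same bullet as the disputed percentage, and lists percentage of planned dose and a reduction flag for each patient and cycle. This stands. A reader might infer that reductions vanish from the exposure reporting; the section does not support that. What these displays do not give is a summarised size of the shortfall relative to plan.

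It can also be said that a within-cycle delivery measure is legitimate and can sit beside a reduction flag tied to the enrollment dose. That is true if it is labelled as such. Here it carries the label starting dose and is the only percentage summarised. The wording could even mean each cycle's Day 1 dose as a percentage of the original dose. That is the less natural reading, and the ambiguity would itself justify a rewrite.

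No formal decision uses this percentage: the MTD rests on DLTs, and the plan tests no hypotheses. This stands too, and limits the weight of the point.

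Three other inferences go too far:

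- **That a reduced patient reads 100% in every later cycle.** Case 3 shows that a later omission or within-cycle reduction still appears.
- **That the percentage contradicts the 80% rules in 6.2, 6.6 and 7.2.1.** Those are mainly evaluability rules for Cycle 1 or the DLT period. In Cycle 1 the Day 1 dose is normally the planned dose, so the two references coincide.
- **That the denominator hides an effect of PF-06747143 on delivery of the backbone chemotherapy.** Section 7.2.1 does require "at least 80% of the planned dose of the PF-06747143 and backbone chemotherapy" for DLT evaluability, but it prescribes no exposure table. Part 2 has no chemotherapy-alone arm, so no choice of denominator would answer that question.

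**Conclusion.** The point holds for the summarised percentage. On its natural reading, the statistic is insensitive by construction to any reduction already in force on Day 1 of a cycle, and it departs from the fixed reference that the same section uses to define a reduction. With all doses given after a reduction from Cycle 2 Day 1, it reads 100% in every cycle, while delivery against plan over four cycles is 92.5%, 81.2% or 62.5% for assumed reductions to 90%, 75% or 50%. These sizes are illustrative, since the SAP states neither the size nor the frequency of reductions, and they assume four planned doses per cycle.

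The consequence is limited to a misleading description of relative dose in later cycles. The occurrence, timing and reasons of reductions stay reported, and no decision rule is affected. The correction is still worth making before the tables are programmed, because it is nearly free and bears on long-term feasibility.

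**What to change.** In 9.2.4:

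1. Reconcile the 21-day cycle stated there with the 28-day cycle stated in Section 2. This comes first, because it sets the number of planned doses per cycle, and the cycle-delay definition depends on it as well.
2. Replace the summarised percentage by the percentage of planned dose, by dose level and cycle: total dose administered in the cycle divided by the total planned for that cycle.
3. State, for both the summary and the listing, that planned means the dose planned at enrollment. The listing carries the percentage but does not say which planned dose it uses.
4. If a percentage of the cycle's Day 1 dose is kept, label it as a within-cycle delivery measure and drop the term starting dose.

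The cost is a few lines of SAP text and one summary of a variable already planned for the listing, with no new data. The downside is that reported relative dose becomes less favourable for patients with reductions, by up to the size of the reduction in each affected cycle.

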#### Prior, Concomitant, and Further Therapies

Prior, concomitant, and further therapies (drug and non-drug treatments) will be coded by the World Health Organization (WHO) medical dictionary. Listings of prior, concomitant, and further therapies will be provided separately.

### 11. APPENDICES

#### 11.1. APPENDIX 1: CATEGORICAL CLASSES FOR ECG AND VITAL SIGNS

## Categories for QTcB and QTcF

QTcB/QTcF	max. ≤450	450< max. ≤480	480< max.≤500	max. >500
(ms)				
QTcB/QTcF	max. < 30	30≤ max. <60	max. ≥60	
(ms) increase				
from baseline				

## Categories for PR and QRS

PR (ms)	max ≥300	
PR (ms) increase	Baseline >200	Baseline ≤200 and
from baseline	and max.	max. ≥50%
	≥25% increase	increase
QRS (ms)	max ≥200	
QRS (ms)	Baseline >100	Baseline ≤100 and
increase from	and max.	max. ≥50%
baseline	≥25% increase	increase

## **Categories for Vital Signs**

Systolic BP (mm Hg)	min. <90	
Systolic BP (mm Hg) change from baseline	max. decrease ≥30	max. increase ≥30
 		
Diastolic BP (mm Hg)	min. <50	
Diastolic BP (mm Hg)	max. decrease ≥20	max. increase ≥20
change from baseline		
Supine pulse rate (bpm)	min. <40	max. >120

Measurements that fulfil these criteria are to be listed in the study report.

#### 11.2. APPENDIX 2: CENSORING DETAILS

Table 4. Progression Free Survival and Duration of Response

Situation	Date of Progression/Censoring 	Outcome		
Inadequate baseline assessment	Start date (C1D1)	Censored		
No on-study assessments	Start date (C1D1)	Censored		
Alive, on treatment  and no Progression	Date of last objective tumor assessment	Censored		
Progression Documented on or between scheduled tumor assessments prior to treatment discontinuation 	Date of first objective tumor assessment showing objective progression	Progressed (Event)		
Treatment discontinuation for undocumented progression	Date of last objective tumor assessment prior to discontinuation 	Censored		
Treatment discontinuation due to toxicity or other reason	Date of last objective tumor assessment prior to discontinuation 	Censored		
Death prior to first planned tumor assessment	Date of death	Death (Event)		
Death without objective progression prior to treatment discontinuation 	Date of death	Death (Event)		
Death or progression after 2 or more missed tumor assessments	Date of last objective tumor assessment prior to the event	Censored		

1: For date of censorship, if a tumor assessment takes place over a number of days (eg, superficial lesions one day, scans another), the last date is used as the assessment date.

**Table 5.** Time to Progression

Situation	Date of Progression/Censoring 	Outcome		
Inadequate baseline assessment	Start date (C1D1)	Censored		
No on-study assessments	Start date (C1D1)	Censored		
Alive, on treatment  and no	Date of last objective tumor assessment	Censored		
Progression	-			
Progression Documented on or	Date of first objective tumor assessment	Progressed (Event)		
between scheduled tumor assessments	showing objective progression			
prior to treatment discontinuation 				
Treatment discontinuation for	Date of last objective tumor assessment	Censored		
undocumented progression	prior to discontinuation 			
Treatment discontinuation due to	Date of last objective tumor assessment	Censored		
toxicity or other reason	prior to discontinuation 			
New anticancer treatment <28 days	Date of last objective tumor assessment	Censored		
after discontinuation of treatment	prior to new anticancer treatment			
without progression				
Death prior to first planned tumor	Start date (C1D1)	Censored		
assessment				
Death without objective progression	Date of last objective tumor assessment	Censored		
prior to treatment discontinuation 	prior to death			
Progression after 2 or more missed	Date of last objective tumor assessment	Censored		
tumor assessments	prior to the event			

1: For censoring date, if a tumor assessment takes place over a number of days (eg, superficial lesions one day, scans another), the last date is used as the assessment date.

2: or within 28 days of discontinuation of treatment.

2: or within 28 days of discontinuation of treatment.

#### 11.3. Appendix 3. Detailed Dose Escalation/De-Escalation Scheme for mTPI Design

#### Number of Patients

#### Number of Toxicities

	1	2	3	4	5	6	7	8	9	10	11	12
0	E	E	E	E	E	E	E	E	E	E	E	E
1	D	D	S	S	S	S	E	E	E	E	Е	E
2		DU	D	D	S	S	S	S	S	S	S	S
3			DU	DU	DU	D	S	S	S	S	S	S
4				DU	DU	DU	DU	DU	D	S	S	S
5					DU	DU	DU	DU	DU	DU	D	S
6						DU						
7							DU	DU	DU	DU	DU	DU
8								DU	DU	DU	DU	DU
9									DU	DU	DU	DU
10										DU	DU	DU
11											DU	DU
12												DU

E=Escalate to the next higher dose
S=Stay at the current dose
D=De-escalate to the next lower dose
DU=The current dose is unacceptably toxic
Probability of target toxicity=0.25

Escalation/De-escalation algorithms for total number of patients treated at the current dose level (current and previous cohorts)

- With 2 patients treated at current dose level
  - o 0 DLT -> escalate
  - o 1 DLT -> de-escalate to the lower dose
  - 2 DLTs -> de-escalate and consider current dose as intolerable
- With 3 patients treated at current dose level
  - o 0 DLT -> escalate
  - o 1 DLT -> remain at the same dose
  - o 2 DLTs -> de-escalate
  - 3 DLTs -> de-escalate and consider current dose as intolerable
- With 4 patients treated at current dose level
  - o 0 DLT -> escalate
  - o 1 DLT -> remain at the same dose

- o 2 DLTs -> de-escalate
- 3-4 DLTs -> de-escalate and consider current dose as intolerable
- With 5 patients treated at current dose level
  - 0 DLT -> escalate
  - o 1-2 DLTs -> remain at the same dose
  - >= 3 DLTs -> de-escalate and consider current dose as intolerable
- With 6 patients treated at current dose level
  - o 0 DLT -> escalate
  - o 1-2 DLTs -> remain at the same dose
  - o 3 DLTs -> de-escalate
  - 4-6 DLTs -> de-escalate and consider current dose as intolerable
- With 7 patients treated at current dose level
  - o 0-1 DLT -> escalate
  - o 2-3 DLTs -> remain at the same dose
  - >= 4 DLTs -> de-escalate and consider current dose as intolerable
- With 8 patients treated at current dose level
  - o 0-1 DLT -> escalate
  - o 2-3 DLTs -> remain at the same dose
  - >= 4 DLTs -> de-escalate and consider currentdose as intolerable
- With 9 patients treated at current dose level
  - o 0-1 DLT -> escalate
  - o 2-3 DLTs -> remain at the same dose
  - o 4 DLTs -> de-escalate
  - 5-9 DLTs -> de-escalate and consider current dose as intolerable
- With 10 patients treated at current dose level
  - o 0-1 DLT -> escalate
  - o 2-4 DLTs -> remain at the same dose
  - >= 5 DLTs -> de-escalate and consider current dose as intolerable
- With 11 patients treated at current dose level
  - o 0-1 DLT -> escalate
  - o 2-4 DLTs -> remain at the same dose
  - o 5 DLTs -> de-escalate
  - 6-11 DLTs -> de-escalate and consider current dose as intolerable
- With 12 patients treated at current dose level
  - o 0-1 DLT -> escalate
  - o 2-5 DLTs -> remain at the same dose

 6-12 DLTs -> de-escalate and consider current dose as intolerable

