**Table 1. Possible Dose Levels** 

Dose Level	PF-06747143 Dose (mg/kg) (QW)
1	0.3
2	1.0
3	3.0
4	10
5	15
6	20

The mTPI method relies upon a statistical probability algorithm, calculated using all patients treated in prior and current cohorts at the same dose level to determine where future cohorts should be on dose escalation, no change in dose, or dose de escalation. The algorithm will stop if any of the following criteria is met:

- the maximum sample size has been achieved (approximately 50 patients total);
- at least 9 patients have been accumulated on a dose that is predicted to be the MTD;
   or
- all doses explored appear to be overly toxic and the MTD cannot be determined.

Although dose levels are capped at 20 mg/kg, this mTPI will continue to operate subject to the constraints detailed above while allowing for doses higher than specified. All clinically relevant adverse events (AEs) and serious adverse events (SAEs) will be reviewed by the Sponsor and Investigators after each dose level is complete to determine if the dose allocation schedule requires modification.

The modified toxicity probability interval (mTPI) design uses a Bayesian statistics framework and a beta/binomial hierarchical model to tailor dose-escalation and de-escalation decisions.(Ref 7) These rules are conceptually similar to those used by the 3+3 design and all thedose-escalation decisions for a given trial and can be pre-calculated under the mTPI design and presented in a two-way table (Appendix 4).

Patients will continue with study treatment until disease progression, patient refusal or unacceptable toxicity occurs. Patients experiencing a DLT may be managed with dose modification (after dose interruption) or discontinuation. Subsequent dose levels may not be opened until all patients entered at the current dose level have been treated and observed for at least one complete cycle and the number of DLTs among those patients in their first cycle has been determined. Intra-patient dose escalation will not be permitted in this study.

#### 2.2. Part 2

Part 2 dose expansion, is an open-label, multi-center, non randomized study to assess the safety and tolerability and preliminary anti-leukemia activity of PF-06747143 in three cohorts (two combination cohorts and one potential cohort of single agent PF-06747143).

Figure 2.

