#### 6.2. 'PER PROTOCOL' Analysis Set

The per protocol analysis set includes all enrolled patients who receive at least one dose of study treatment at the dose level of MTD and who do not have major treatment deviations during first cycle. Patients with major treatment deviations in Cycle 1 are not evaluable for the MTD assessment and may be replaced. Major deviations include failure to satisfy major entry criteria (eg, confirmation of the target disease population; signed informed consent), administration of less than 3 out of the 4 doses in Cycle 1 or 80% of the planned Cycle 1 dose (provided that the reduction is not due to toxicity attributable to PF-06747143) or use of

other anti-cancer/anti-leukemia treatments during the active treatment and disease follow up phases other than as defined/allowed in this protocol.

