#### 7.2.2. MTD Definition

The MTD would be any doses with true toxicity probabilities in the Equivalence Interval (EI) where the EI is defined as [20%-30%].

In practice, the MTD will be the highest dose associated with the occurrence of DLTs  $\leq$ 33% (eg, 3/9 evaluable patients experience a DLT during the first treatment cycle).

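### The mTPI table counts all patients treated at a dose, while DLT and MTD assessment rests on evaluable patients; a non-evaluable patient without a DLT can make the decision less cautious

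*SAP*

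**What the plan says.** Two places define the count that enters the mTPI, and both use treated patients. Section 2.1.1.2 (text below Table 1) says the algorithm is "calculated using all patients treated in prior and current cohorts at the same dose level". Appendix 3 (Section 11.3) introduces its look-up rules as "Escalation/De-escalation algorithms for total number of patients treated at the current dose level (current and previous cohorts", and each bullet that follows is again indexed by patients treated. The stopping criterion in Sections 2.1.1.2 and 4.2.1, and the minimum in Section 5, ask for 9 patients at the MTD without saying which patients count.

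Other sections work with a narrower group:

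- Section 7.2.1: patients who receive less than 80% of the planned dose "in the DLT assessment period are considered not evaluable for DLT and will be replaced". Those who leave early "may be replaced if they terminate study participation earlier than 28 days without experiencing a DLT", although for some of them "the patient might be deemed evaluable if the Investigators and Sponsor agree".
- Section 6.2: patients with major Cycle 1 treatment deviations "are not evaluable for the MTD assessment and may be replaced". Section 6.6 also makes them not evaluable for MTD.
- Section 7.2.2 illustrates the MTD with "3/9 evaluable patients experience a DLT during the first treatment cycle".
- Section 9.2.1 summarises DLTs by dose level on the Per Protocol set.

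No section says that a non-evaluable or replaced patient is taken out of the count used to read the table.

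**The concern.** The same dose level has two denominators: treated patients for escalation, evaluable patients for the MTD. A patient who left early or was under-dosed, and had no DLT, has not shown that the dose is tolerated. On the treated count that patient nevertheless enters the table as one more patient without a DLT. If the replacement is then added rather than substituted, the count exceeds the number of patients who carry information. The 9-patient stop could likewise be met with fewer than 9 evaluable patients.

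At stake are the Part 1 primary endpoint, the MTD, and the start of Part 2, which depends on a Part 1 dose level being cleared.

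**Working it through.** **Inputs.** Target DLT rate 0.25 and equivalence interval 0.20 to 0.30 (Sections 2.1.1.2 and 4.2.1); dose-exclusion threshold 0.975 (Section 4.2.1); cohorts of 2 to 4, target 3 (Section 2.1.1.2); the printed table for 1 to 12 patients (Appendix 3). The entries for 6 DLTs in 7 to 12 patients are taken from the bullet list. The SAP names a beta/binomial model without prior parameters, so Beta(1,1) is an assumption.

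**Step 1: reproduce the table.** With x DLTs in n patients the posterior is Beta(1+x, 1+n−x). The unit probability mass (UPM) is the posterior probability of an interval divided by its length; the lengths are 0.20 (escalate, E), 0.10 (stay, S) and 0.70 (de-escalate, D). The largest UPM decides.

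- 1/3: E 0.904, S 1.675, D 0.931, so stay.
- 3/6: E 0.167, S 0.927, D 1.249, so de-escalate.
- 3/7: E 0.281, S 1.378, D 1.151, so stay.

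The E/S/D direction agrees with all 90 printed cells. At 1/2 there is an exact tie: 0.112/0.10 = 1.12 for S and 0.784/0.70 = 1.12 for D. The printed table resolves it to D. The DU flags (unacceptably toxic) agree in all 90 cells only with a threshold of 0.95. At the stated 0.975, four DU cells (3/5, 4/7, 4/8, 5/10) would be D. The next two steps use the printed table alone and need no model for the table.

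**Step 2: add one non-evaluable patient without a DLT.** This compares the printed decision at (x, n) with that at (x, n+1). For n from 1 to 11 there are 11 such steps with no DLT and 11+10+…+1 = 66 with at least one, 77 in all.

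| Change | Steps (DLTs/patients) | Number |
|---|---|---|
| D to S | 1/2→1/3, 2/4→2/5, 3/6→3/7, 4/9→4/10, 5/11→5/12 | 5 |
| S to E | 1/6→1/7 | 1 |
| DU to D | 2/2→2/3, 3/5→3/6, 4/8→4/9, 5/10→5/11 | 4 |
| None | all others | 67 |
| More cautious | none | 0 |

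With the 0.975 threshold the number of changes is still 10; three of the four DU-to-D steps move to other cells.

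**Step 3: size at a given step.** With n evaluable patients and an assumed true DLT rate p, the number of DLTs is Binomial(n, p). P(D or DU) is then read in column n and in column n+1.

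| Evaluable, read as | p = 0.30 | p = 0.40 |
|---|---|---|
| 2, as 3 | 0.510 → 0.090 | 0.640 → 0.160 |
| 3, as 4 | 0.216 → 0.216 | 0.352 → 0.352 |
| 4, as 5 | 0.348 → 0.084 | 0.525 → 0.179 |
| 6, as 7 | 0.256 → 0.070 | 0.456 → 0.179 |

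For 2 read as 3 at p = 0.40: at least 1 DLT is needed in column 2, 1 − 0.6² = 0.640; both patients must have one in column 3, 0.4² = 0.160. For 6 read as 7 the requirement rises from at least 3 DLTs to at least 4, and P(escalate) at p = 0.40 rises from 0.6⁶ = 0.047 to 0.047 + 6 × 0.4 × 0.6⁵ = 0.233.

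**Step 4: what a bare reference to Section 7.2.1 would do.** Its 80% rule has no exception for toxicity; Sections 6.2 and 6.6 have one. A patient under-dosed because of a DLT would then leave both numerator and denominator. On the printed table 1/3 (S) becomes 0/2 (E), 2/4 (D) becomes 1/3 (S), 3/6 (D) becomes 2/5 (S) and 4/9 (D) becomes 3/8 (S).

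**The case against.** The best defence is that evaluable patients were meant. Replacement ordinarily means substitution, not addition. Sections 6.2 and 6.6 exclude Cycle 1 deviators from MTD assessment, which is what the table serves. Section 2.1.1.2 holds the next level until all patients at the current one have been observed for a full cycle, and Section 4.2.1 ties allocation to a completed Cycle 1 safety assessment. This makes the evaluable reading plausible, so a reader should not infer that the SAP deliberately chose a treated-patient analysis. But none of these passages defines the table count or deals with under-dosed patients, and both places where the count is defined say treated.

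A reader might also infer that every non-evaluable patient enters as DLT-free and that the error can run only one way. The SAP does not support that. Under Section 7.2.1 a patient under-dosed because of a DLT is also non-evaluable, and on a treated count that DLT is kept. Some early leavers may be deemed evaluable by agreement, and a replacement patient can have a DLT. The one-way result holds only for non-evaluable patients without a DLT.

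On size, the objection largely stands. Most steps do not change, including 3 evaluable patients read as 4. Four of the ten changes still de-escalate and alter only whether the dose is excluded. The probabilities in step 3 assume that exactly one such patient is present; they are not operating characteristics of the design.

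**Conclusion.** The inconsistency is real and concerns the rule that drives Part 1. Followed as written, counting one non-evaluable patient without a DLT changes 10 of 77 look-ups, all towards less caution; six of these alter the next dose assignment. Where a step is affected the effect can be large: at an assumed true rate of 0.40, P(D or DU) falls from 0.640 to 0.160 with 2 evaluable of 3 treated, a situation that a single non-evaluable patient produces in a target-size cohort.

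The look-ups rest on the printed table alone, the probabilities on assumed DLT rates. The 10 of 77 counts table cells and is not a probability. The SAP gives no non-evaluable rate, so it does not support a claim about how often decisions would change or how far the MTD would be biased.

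**What to change.** Reconcile Sections 2.1.1.2, 4.2.1, 5, 6.2, 6.6, 7.2.1, 7.2.2 and Appendix 3 so that the table's column count, the 9-patient stop and the MTD definition share one denominator, DLT-evaluable patients. Define these as every treated patient with a DLT in the assessment period, plus every patient without a DLT who meets the observation and dosing requirements of Section 7.2.1. State that a replaced patient without a DLT is not counted.

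Reconcile the 80% rule in Section 7.2.1 with the toxicity exception in Sections 6.2 and 6.6, so that no patient with a DLT drops out of the count. Without this, pointing the table to Section 7.2.1 could cause the losses shown in step 4.

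The cost is SAP wording; the DLT event criteria and the table cells stay as they are. The downside is that a dose level may have to wait for a replacement patient before a decision.
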